- ^s MRI scans are to include vMRI and fMRI sequences and will be read by an approved central reader. MRI imaging will be conducted on separate days from the scheduled visits. MRI imaging should be conducted within the 7 days before Visits 9 and 13. In the event of an Unscheduled Visit, the investigator in consultation with the Medical Monitor will determine whether or not a safety MRI should be conducted. If an ED Visit takes place, an MRI is to be conducted if not already performed during the preceding 90 days.
- ^t PET scanning (if subject has consented to optional substudy) will be performed with a locally approved amyloid β imaging agent (eg, Neuroceq, if available) or an agent under clinical investigation if no agents are approved locally; the imaging agent must remain unchanged for an individual subject throughout the study. A PET scan will only be performed at an ED Visit if the subject has been treated with study drug for at least 39 weeks and at least 6 months has elapsed since the prior PET scan was performed. (revised per Amendment 03)
- ^u Site staff will contact the subject or the study partner the day before the PK blood sampling to provide instructions that subjects must not take their study drug at home on the day of the PK blood sampling. During this telephone contact with the subject or the study partner, the site staff should document the time that the subject took their study drug that day, ie, the day before the PK blood sampling.
- ^v Two plasma PK samples will be obtained: 1 sample at predose (trough) and another sample 1 to 6 hours postdose at Visits 3, 4, 6, 7, 9, and 11 and another sample 4 to 8 hours postdose at Visit 13 (or ED). Therefore, subjects or their study partners must be instructed not to take their study drug at home on the day the PK sampling is performed. Instead, subjects will take the study drug at the clinic after collection of the predose PK sample. At Visit 13 (or ED) the PK blood sample should be collected shortly before or after completing the LP for subjects participating in the CSF substudy. If at an ED Visit, the subject has already stopped study drug, then no dosing will take place, but the trough PK sample will still be collected. For subjects participating in the CSF substudy who have stopped taking study drug prior to the ED visit, the LP should be performed at approximately the same time as at the Screening Visit, and then a trough PK sample will be collected either shortly before or shortly after the LP.
- ^w PD and exploratory biomarker blood samples should be collected at fasting or at least 2 hours after the most recent meal and, as far as is feasible, samples should be taken at the same time of day at all visits. Samples should be taken predose at Visits 2, 3, 4, 6, 7, 9, 11, 13 (or ED), 14, and 15. (revised per Amendments 02 and 03)
- ^x For subjects who consent to participate in the CSF longitudinal substudy. Visit 13 (or ED) also includes blood PK and PD assessments and so the subject will be dosed at the clinic on these days. A CSF sample will be collected by LP between 4 and 8 hours postdose and at the same time of day as the subject's Screening LP (± 1 hour). The CSF sample will be taken with the subject fasting (preferred) or at least 2 hours after the most recent meal. A gravity drip collection method must be used. If performed on the same day as the cognitive tests, the LP will be performed after the cognitive tests; the subject should rest and drink some fluid to hydrate after the cognitive tests and before the LP. Subjects will be encouraged to stay at the site after completion of LP for medical observation. The CSF sample will not be taken at the ED Visit if this visit occurs within 3 months of a previous CSF sample. If at an ED Visit, the subject has already stopped study drug, then no dosing will take place, but the CSF sample will still be collected unless it was already collected within the past 3 months. Subjects receiving concomitant anticoagulation/antiplatelet therapy should have prothrombin time and INR (derived from prothrombin time) prior to LP; if they are assessed by the investigator to be at risk for bleeding, they are to be excluded from CSF collection. Note that subjects who are assessed by both amyloid PET and CSF are required to wait for a minimum of 48 hours between the 2 procedures. (revised per Amendment 01)
- ^y Subjects reporting AEs relating to abnormal dreams, nightmares, or sleep terror will be questioned on the nature, frequency, and impact of these events.
- ^z AEs that may signal drug abuse potential require a more detailed follow-up through completion of a specific eCRF form (Possible drug abuse potential form/ questionnaire). Similarly, AEs reported during the first 4 weeks following the last dose of study drug that might indicate physical dependency also require a more detailed follow-up through completion of the same eCRF form. Categories and examples of AEs indicating signals of possible drug abuse are provided in [Appendix 3](#) and a more comprehensive list is provided in the eCRF Completion Guidelines. (revised per Amendments 01 and 03)
- ^{aa} The first dose of study drug will be given to the subject at the study site. Subjects will be encouraged to stay at the site for observation for at least 30 minutes following their first dose of study drug. The duration of this observation period can be extended at the Investigator's discretion, eg, if warranted by medical history or concomitant medication. (revised per Amendment 03)

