In the event that a subject develops moderate to severe oral or genital herpes, study drug administration should be interrupted for a maximum period of 4 weeks. Subjects who develop a mild case of oral or genital herpes may remain on study drug even if the event lasts more than 72 hours. Subjects who recover from moderate to severe oral or genital herpes within 4 weeks may resume treatment if it is deemed appropriate by the investigator after consultation with the Medical Monitor. Subjects should permanently discontinue study drug if the oral or genital herpes has not resolved within 4 weeks or returns during rechallenge. (revised per Amendment 02)

Subjects who discontinue study drug early must complete the ED Visit (within 7 days of the last dose of study drug) and the Follow-Up Visits (1 and 3 months after the last dose of study drug). These Follow-Up Visits will be conducted to monitor efficacy and safety parameters after early withdrawal from the study or discontinuation of study drug.

All subjects who discontinue study drug before reaching 12 months of treatment will also be asked to return to the clinic for a 12-month clinical assessment and then again at 24 months. Subjects who discontinue treatment between 12 and 24 months of treatment will be asked to return to the clinic for a 24 month clinical assessment. Subjects who discontinue early from study drug are considered “on study” as long as they continue to return for their regularly scheduled clinical assessments at 12 and 24 months as outlined above, at which efficacy and quality of life will be assessed along with concomitant medications and AEs. However, subjects who discontinue study drug early are not considered to have ‘completed’ the study as a final Subject Disposition.

The primary reason for discontinuation and all other reason(s) contributing to the subject's discontinuation from study drug(s) should be collected on the ED from study drug electronic case report form (eCRF) page. In addition, the date of last dose of study drug(s) will be recorded on the Study Drug Dosing eCRF page. If a subject discontinues study treatment and the study at the same time, the end-of-study procedures (Final Visit) will be followed (see [Section 9.5.5](#)).

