ADAS-cog₁₄ = Alzheimer’s Disease Assessment Scale - Cognitive subscale (14 items), CBP = child-bearing potential, CDR = Clinical Dementia Rating scale, CMV = cytomegalovirus, CNS = central nervous system, CSF = cerebrospinal fluid, C-SSRS = Columbia Suicide Severity Rating Scale, ECG = electrocardiogram, ED = Early Discontinuation, EQ-5D = EuroQol-5 Dimensions, FAQ = Functional Assessment Questionnaire (also known as the Functional Activities Questionnaire), fMRI = functional MRI (to be performed task free at resting state), HSV1 = herpes simplex virus 1 (orolabial herpes), HSV2 = herpes simplex virus 2 (genital herpes), INR = International Normalized Ratio, LP = lumbar puncture, MMSE = Mini Mental State Examination, MRI = magnetic resonance imaging, NPI = Neuropsychiatric Inventory, PBMC = peripheral blood mononuclear cell, PD = pharmacodynamics, PET = positron emission tomography, PK = pharmacokinetics, QOL-AD = Quality of Life in Alzheimer’s Disease, UNS = unscheduled, vMRI = volumetric MRI.

^a A window of ±3 days will be permitted for Visits 3 and 4. A window of ±7 days will be permitted for Visits 5 and 6. A window of ±10 days will be permitted for Visit 7 to 13 inclusive. A window of ±3 days will be permitted for the Follow-Up Visits. If use is made of the permitted visit windows, every effort should be made to bring the subject back in line with the “weeks elapsed since 1st dose” at subsequent visits.

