^b Subjects who discontinue taking study drug prematurely for any reason will undergo an ED Visit within 7 days of their last dose of study drug. In addition, Follow-Up Visits will be scheduled 4 and 12 weeks after the last dose of study drug (Visit 14 and Visit 15, respectively). Subjects who discontinue study drug before reaching 12 months of treatment will also be asked to return to the clinic for a 12 month clinical assessment and then again at 24 months. Subjects who discontinue treatment between 12 and 24 months of treatment will be asked to return to the clinic for a 24 month clinical assessment. Subjects who discontinue early from study drug are considered “on study” as long as they continue to return for their clinical assessments at 12 and 24 months as outlined above, at which efficacy (MMSE, CDR, ADAS- cog₁₄) and quality of life (EQ-5D, QOL-AD and Zarit’s Burden Interview) will be assessed along with concomitant medications and AEs. These 12 and 24 month clinical assessment visits do not need to be attended if they fall within 8 days (visit window) after the ED Visit or within ±8 days of either of the Follow-Up Visits (Visit 14 and Visit 15).

- ^c All subjects, regardless of whether they complete all 24 months of treatment or discontinue study drug prematurely, will complete 2 posttreatment Follow-Up Visits; one 4 weeks after the last dose of study drug and a second 12 weeks after the last dose of study drug (Visit 14 and Visit 15 respectively). If clinically indicated, more frequent safety assessments can be made as UNS assessments or visits during the posttreatment Follow-Up Period. Subjects who have a Grade 2 or greater lymphocytopenia (less than 800/mm³) during the follow-up period (ie, at either Visit 14 or Visit 15) should have ALC measured every 4 weeks until resolution or confirmation of a non drug-related cause of the lymphocytopenia. ALC will be derived from the CBC with differential representing the normal lymphocytes (with atypical lymphocytes removed and presented as a separate count if they are present) and calculated by the white blood cell count × percentage of lymphocytes. (revised per Amendment 01)

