9.7.1.1.3 EXPLORATORY ENDPOINTS

The exploratory endpoints of the study are:

- Time to change of concomitant AD treatment (ie, dose increase and/or initiation of treatment with AChEI or memantine after randomization) by 24 months
- The proportion of subjects at 24 months who received dose increases and/or initiation of treatment with AChEI or memantine after randomization
- The rate of change over time (mean slope) based on NPI-10 item score over 24 months
- Change from baseline in NPI-10 item at 24 months
- Change from baseline in EQ-5D (subject self-reported, study partner self-reported, and subject measured by proxy) and QOL-AD (subject and study partner) at 24 months
- Change from baseline in Zarit's Burden Interview at 24 months

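### When Visit 14 or 15 replaces an early stopper's 12- or 24-month return visit, EQ-5D, QOL-AD and Zarit are not collected

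*Protocol*

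**What the plan says.** Footnote b to Table 4 (Section 9.5.2.1) sets the follow-up of early stoppers:

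- **Timing of follow-up.** "Follow-Up Visits will be scheduled 4 and 12 weeks after the last dose of study drug (Visit 14 and Visit 15, respectively").
- **Stop in the first year.** Two return visits are requested, one at each anniversary: "Subjects who discontinue study drug before reaching 12 months of treatment will also be asked to return to the clinic for a 12 month clinical".
- **Stop in the second year.** One return visit is requested: "Subjects who discontinue treatment between 12 and 24 months of treatment will be asked to return to the clinic for a 24 month clinical assessment".
- **Content of the return visit.** MMSE, CDR and ADAS-cog14, and "quality of life (EQ-5D, QOL-AD and Zarit’s Burden Interview) will be assessed along with concomitant medications and AEs".
- **Waiver.** A return visit may be left out where the dates are close: "do not need to be attended if they fall within 8 days (visit window) after the ED Visit or within ±8 days of either" (Visit 14 or Visit 15).

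The Table 4 grid places CDR, MMSE, ADAS-cog14 and FAQ at Visits 14 and 15. The EQ-5D, QOL-AD and Zarit rows are marked at Visits 7, 9, 11, 13 and ED only.

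Sections 9.3.3 and 9.5.5 also request the return visits, "at which efficacy and quality of life will be assessed along with concomitant medications and AEs", and mention no waiver. Section 9.7.1.1.3 lists the 24-month changes in EQ-5D (three versions), QOL-AD (two versions) and Zarit as exploratory endpoints, for example "Change from baseline in Zarit's Burden Interview at 24 months". Section 9.7.1.6.3 tests each at two-sided 0.05.

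**The concern.** The waiver makes sense only if the visit that stands in collects what the waived visit would have collected. The ED Visit does. Visits 14 and 15 do so for CDR, MMSE and ADAS-cog14, but not for the three questionnaires. A site following footnote b as written may therefore have the subject in clinic within 8 days of the month-24 date and still record no quality-of-life or partner-burden value.

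This is a data-collection rule, so no analysis plan can recover what was never asked. The subjects concerned are early stoppers, the group for whom the return visits were created.

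**Working it through.** **Inputs.** From Table 4: Visit 8 = Day 274, 12 months (Visit 9) = Day 365, Visit 12 = Day 638, 24 months (Visit 13) = Day 729, Visit 14 = Day 757, Visit 15 = Day 813. From footnote b: follow-up at last dose + 28 and + 84 days, waiver limit 8 days. From footnote a: "A window of ±10 days will be permitted for Visit 7 to 13 inclusive", and ±3 days for the Follow-Up Visits. From Section 9.7.2: 1330 subjects, 30% dropout.

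**1. Reproduce the plan's dates.** 729 + 28 = 757 and 729 + 84 = 813, as in Table 4.

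**2. Which last-dose days trigger the waiver.** Let L be the last-dose day and T the target day.

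- Via Visit 14: |T − (L + 28)| ≤ 8, so L runs from T − 36 to T − 20.
- Via Visit 15: |T − (L + 84)| ≤ 8, so L runs from T − 92 to T − 76.

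| Target | Via Visit 15 | Via Visit 14 | Days in total |
|---|---|---|---|
| 24 months (729) | 637-653 | 693-709 | 17 + 17 = 34 |
| 12 months (365) | 273-289 | 329-345 | 17 + 17 = 34 |

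**3. Stops at scheduled visits, nominal dates.**

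- Visit 12: 638 + 84 = 722, and 729 − 722 = 7 days. The 24-month visit may be skipped.
- Visit 8: 274 + 84 = 358, and 365 − 358 = 7 days. The 12-month visit may be skipped. The 24-month date is 729 − 358 = 371 days after Visit 15, so that visit is still requested.

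**4. Effect of the visit windows.** With ±10 days, Visit 12 can fall on Days 628-648. If the last dose is on the visit day and Visit 15 is on time, only Days 637-648 qualify: 12 of 21. Allowing also ±3 days for Visit 15, 84 of 21 × 7 = 147 combinations qualify, or 57%. The figures for Visit 8 are the same.

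**5. Number of subjects.** The documents give no distribution of stopping times. Assume they are uniform over Days 1-728, and that all 0.30 × 1330 = 399 dropouts are drug stoppers who would otherwise return.

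- 24-month values at risk: 34/728 = 4.7%, and 399 × 34/728 = 18.6, about 19 subjects (19/1330 = 1.4% of those randomised).
- If only half of the 399 would have returned: 18.6/2 = 9.3, about 9.
- 12-month values only: another 34 days, so about another 19 at most on the same assumptions.

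**6. What remains for subjects who miss month 24.** The ED Visit, within 7 days of last dose, collects all three instruments. For L = 637-653 it falls on Days 637-660, which is 69 to 92 days before Day 729. For L = 693-709 it falls on Days 693-716, which is 13 to 36 days before.

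**The case against.** The best defence is that little is lost. The endpoints are exploratory, the number of subjects is small, the waiver only permits the visit to be skipped, and an ED value exists from at most about three months before month 24. All of that stands and limits the size of the point. It does not remove the gap: the endpoint is the 24-month value, and the subject may be in clinic within 8 days of that date.

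Five stronger readings are tempting, and the documents do not support them.

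- **That a Visit 8 stopper loses the 24-month endpoint.** Footnote b asks anyone stopping before 12 months back at both 12 and 24 months. Only the 12-month values can be skipped, and no listed endpoint for these instruments is at 12 months.
- **That everyone stopping at Visit 12 is affected.** The nominal gap is 7 days against a limit of 8, and the visit windows move many dates outside it.
- **That the primary endpoint suffers.** CDR is collected at Visits 14 and 15.
- **That the results become clearly weighted towards those who tolerated treatment.** The waiver depends on the calendar day of the last dose, not on tolerability or outcome. Under the uniform assumption, 95.3% of stop days leave the 24-month request in place. Any bias from this source should be slight.
- **That the 8 days should be aligned with the ±10 days of footnote a.** Footnote a governs scheduled Visits 7 to 13, whereas footnote b can be read as a separate tolerance for return assessments. A 10-day limit would also enlarge the loss, from 4 × 17 = 68 stop days to 4 × 21 = 84.

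**Conclusion.** The point holds as an inconsistency between footnote b and the Visit 14 and 15 columns of Table 4. Its reach is limited to the last-dose ranges in the table above, and only the ranges around Visit 12 and later touch a listed endpoint.

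The figure of about 19 subjects is an order of magnitude. It is generous in treating the whole dropout allowance as drug stoppers who would otherwise return, since anyone who leaves the study has no return visit to waive. It would rise if stops cluster near Visit 12. The calendar ranges need neither assumption: they follow from the protocol's own days, with Visits 14 and 15 held on time. This is a minor point, worth correcting because the correction is cheap and the missing data cannot be recovered later.

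**What to change.** Add to Table 4, footnote b: when Visit 14 or Visit 15 replaces a 12- or 24-month assessment, EQ-5D, QOL-AD and Zarit's Burden Interview are administered at that visit, and the visit is recorded as the month-12 or month-24 assessment. Alternatively, limit the waiver to the ED Visit, which already collects all three. Leave the 8-day limit as it is, and carry the waiver into Sections 9.3.3 and 9.5.5 so that the text and the table agree.

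The cost of the first option is three questionnaires at a visit the subject already attends, for a few tens of subjects at most. Section 9.5.1.6 already lets the investigator accept telephone contact with the study partner for these instruments. The second option costs those subjects one extra visit close to a follow-up visit.

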9.5.2.2 Description of Procedures/Assessments Schedule

Please refer to [Table 3](#) and [Table 4](#) for the timings of the procedures and assessments to be performed during the study. Screening assessments will be organized into 5 tiers (see [Table 3](#)). See [Section 9.5.1](#) for a full description of the procedures and assessments to be performed during this study.

Table 5 presents the number of blood and CSF samples, and the estimated total volume of blood and CSF that will be collected throughout the study. (revised per Amendment 02) Additional samples may be taken at the discretion of the investigator if the results of any tests fall outside reference ranges or if clinical symptoms necessitate testing to ensure subject safety. Actual specimen volumes may vary based on local regulations. (revised per Amendment 02)

Table 5 Summary of Estimated Blood and CSF Sample Volumes

Assessment	Total Number of Collection Time Points	Sample Volume, Number of Time Points × Volume per Collection (mL)			Total Volume ^a (mL)
		Screening Visits	Visit 2 Baseline (predose) (revised per Amendment 03)	Treatment and Follow-Up Periods	
Blood					
Clinical chemistry (revised per Amendments 02 and 03)	15	1×2.5 mL	1×2.5 mL	13×2.5 mL	37.5 mL
Serum pregnancy test at Screening (females of child-bearing potential only)	0	can use blood drawn for clinical chemistry	can use blood drawn for clinical chemistry	none	no additional volume
Hematology (revised per Amendment 03)	15	1×2 mL	1×2 mL	13×2 mL	30 mL
Coagulation (revised per Amendments 02 and 03)	15	1×1.8 mL	1×1.8 mL	13×1.8 mL	27 mL
Thyroid function tests (thyroid stimulating hormone, free triiodothyronine and free thyroxine)	1	1×5 mL	none	none	5 mL
Viral screen at Screening (Hepatitis B and C) (revised per Amendment 02)	1	1×2.5 mL	none	none	2.5 mL
Viral characterization at Visit 2 (previous exposure to CMV, HSV1, HSV2, etc.) (revised per Amendments 02 and 03)	1	none	1×3.5 mL	none	3.5 mL

Table 5 Summary of Estimated Blood and CSF Sample Volumes

Assessment	Total Number of Collection Time Points	Sample Volume, Number of Time Points × Volume per Collection (mL)			Total Volume ^a (mL)
		Screening Visits	Visit 2 Baseline (predose) (revised per Amendment 03)	Treatment and Follow-Up Periods	
Vitamin B12 at Screening (revised per Amendments 02 and 03)	0	can use blood drawn for TFT	none	none	no additional volume
Blood for immunologic assessments, including isolation of PBMCs for storage and later testing (revised per Amendment 03)	14		1×20 mL	13×20 mL	280 mL
Blood for immune status (revised per Amendment 03)	8	none	1×5 mL	7×5 mL	40 mL
AD diagnostics and exploratory biomarker (revised per Amendment 03)	1	1×6 mL	none	none	6 mL
PD and exploratory biomarker sample (revised per Amendments 01, 02, and 03)	10	none	1×12 mL	9×6 mL	66 mL
PK analysis (revised per Amendment 02)	7	none	none	14×2 mL	28 mL
Pharmacogenomic sample (revised per Amendments 01 and 02)	1	1×6 mL	none	none	6 mL
All blood samples, total volume collected (revised per Amendments 01, 02 and 03)		25.8 mL	46.8 mL	458.9 mL	531.5 mL
CSF					
Amyloid eligibility	1	1×12 mL	none	none	12 mL
PD / PK (optional longitudinal substudy)	1	none	none	1×12 mL	12 mL

Note: Actual volumes may be less, based on regional differences in Central Laboratories.

AD = Alzheimer's disease, CMV = cytomegalovirus, CSF = cerebrospinal fluid, HSV1 = herpes simplex virus 1 (orolabial herpes), HSV2 = herpes simplex virus 2 (genital herpes), PBMCs = peripheral blood mononuclear cells, PD = pharmacodynamics, PK = pharmacokinetic, TFT = thyroid function Test.

a: The total volume includes all blood/CSF collection from Screening through Week 117 (Followup Visit) ; actual volume may vary based on local regulations. (revised per Amendment 02)

